4.1 Contacts by the Jaeb Center for Health Research and Sites

The Jaeb Center serves as the PEDIG Coordinating Center. The Jaeb Center will be provided with the parent's contact information. The Jaeb Center may contact the parents of the subjects. Permission for such contacts will be included in the Informed Consent Form. The principal purpose of the contacts will be to develop and maintain rapport with the subject and/or family and to help coordinate scheduling of the outcome examinations.

The site investigator or coordinator will contact the parents of each subject after the first week of the study to encourage compliance with treatment and to confirm that there are no technical problems playing the binocular game for those assigned to binocular treatment.

4.2 Game Alerts

In the event that the subject is unable to successfully play the game for whatever reason (e.g., failure of amblyopia to improve, worsening of amblyopic eye, inattention of subject), contrast of the fellow eye will automatically decrease in 10% increments, to as low as 10%, which corresponds to the lower limit of the visible threshold for viewing objects on the screen. If the game settings remain at 10% for a period of 7 days, the game will show an alert for parents to contact their eye care provider. Investigators should assess the cause for the inability to play the game. As appropriate, investigators may choose to examine the subject at their discretion and contact the Jaeb center for technical assistance if deemed necessary. Investigators will offer encouragement to the child and parents to continue treatment as best they are able.

4.3 Subject Withdrawals

Parents may withdraw their child from the study at any time. This is expected to be a very infrequent occurrence in view of the study design's similarity to routine clinical practice and short duration. If the parents indicate that they want to withdraw their child from the study, the investigator personally should attempt to speak with them to determine the reason. If their interest is in transferring the child's care to another eye care provider, every effort should be made to comply with this and at the same time try to keep the child in the study under the new provider's care.

4.4 Management of Refractive Error

Because of the short duration of the study and the requirement to have a cycloplegic refraction within 7 months prior to enrollment, no cycloplegic refraction is mandated during the study. Nevertheless, whenever the investigator suspects that refractive error may not be corrected according to study guidelines, a cycloplegic refraction should be performed. Change in spectacle correction is at investigator discretion, but must be prescribed according to the guidelines described in *section 2.2.1*.

4.5 Management of Strabismus

Because of the short duration of the study and the age group being studied, strabismus surgery is not allowed prior to the end of the study (at 16 weeks). If surgery is performed that occurrence will be recorded in the comment section of the Follow-up Examination Form.

If treatment precipitates the development of a manifest ocular deviation (e.g., esotropia) and/or diplopia, the parent will be advised to have the subject see the investigator as soon as possible. If a new manifest deviation is confirmed on examination, the decision as to whether to continue or discontinue therapy will be left to the investigator's and parent's decision. If the investigator determines that binocular diplopia is present, continuation of treatment is also at the discretion of the investigator and parent(s). If amblyopia treatment is to be discontinued during the study, a Protocol Chair should be called to discuss the case. Subjects discontinuing treatment during the study will continue to be seen for the remaining regularly scheduled study visits.

4.6.2 Risks of Examination Procedures

The procedures in this study are part of daily eye care practice in the United States and pose no known risks. As part of a routine usual-care exam, the subject may receive cycloplegic/dilating eye drops.

4.6.3 Risks of Patching

If skin irritation occurs, the parent will be advised to put an emollient on the skin and discontinue use of the patch for a day.

Patching could potentially decrease the visual acuity in the fellow eye, although this is almost always reversible. However, this occurrence is extremely unlikely since the fellow eye will have the majority of the day without occlusion and we have not observed long lasting decrease in visual

acuity in any previous study of 2 hours of daily patching. The diagnosis and management of reverse amblyopia is left to the investigator's judgment.

4.6.4 Delay in Use of Traditional Amblyopia Treatment

The subjects in the binocular computer game treatment group will not be able to perform any patching, atropine, Bangerter filter, or vision therapy treatment during the study. Subjects will continue in the study for a maximum of 16 weeks. Subjects in the patching group will not be able to start any additional treatment or change the duration of patching during the study.

4.7 Reporting of Adverse Events

No surgical procedures are part of the protocol. There are no expected long-term adverse events associated with playing the computer game on the iPad. Investigators will abide by local IRB reporting requirements.

4.7.1 Risk Assessment

It is the investigators' opinion that the protocol's level of risk falls under DHHS 46.404 which is research not involving greater than minimal risk.

4.8 Discontinuation of Study

The study may be discontinued by the Steering Committee (with approval of the Data and Safety Monitoring Committee) prior to the preplanned completion of enrollment and follow-up for all subjects.

4.9 Travel Reimbursement

Parents of each subject will be compensated \$50 per visit (by check, merchandise card, or money-card) for completion of each protocol-specified visit, for a maximum of \$250. If there are extenuating circumstances, and the subject is unable to complete study visits without additional funds for travel costs, additional funds may be provided.

4.10 Study Costs

The subject or his/her insurance provider will be responsible for the costs that are considered standard care.

Because the treatment used in the study is not standard, the enrollment, 4-, 8-, 12-, and 16-week follow-up visits are not considered standard of care and will be paid for by the study. The cost of the patches and the binocular game treatment related equipment will also be paid for by the study; however the iPad will need to be returned upon study completion. Cost of changing or replacing prescription glasses (or contact lenses) during the study will not be paid for by the study as spectacle correction is standard care.

4.11 Offer of Binocular Treatment to Children Assigned to Patching (at Conclusion of Study)

To reduce the potential disincentive to participation because there is only a 50% chance of receiving the novel binocular treatment at enrollment, subjects assigned to the patching group with residual amblyopia at the conclusion of their participation in the study will be offered 16 weeks of binocular game therapy using a study iPad (at no cost). Subjects (originally assigned to patching) who elect

to pursue 16 weeks of binocular treatment after study completion, will return the iPad devices to the site at the conclusion of that additional treatment. No data will be collected from these subjects.

CHAPTER 5: SAMPLE SIZE ESTIMATION AND STATISTICAL ANALYSIS

The approach to sample size and statistical analyses are summarized below. A detailed statistical analysis plan will be written and finalized prior to the completion of the study.

5.1 Definition of Subject Cohorts

The study will enroll two cohorts of subjects with identical eligibility criteria, apart from age at time of randomization:

- Younger Cohort: children aged 5 to < 13 years
- Older Cohort: children aged 13 to <17 years

These cohorts will be analyzed separately as the objectives differ.

5.2 Sample Size Estimation

Sample size estimates for each age cohort were based on data from previous ATS patching studies, limited to subjects meeting the visual acuity eligibility criteria for the current protocol.

5.2.1 Younger Cohort (Children 5 to <13 years of age)

The standard deviation for change in amblyopic eye visual acuity at 16-weeks was estimated to be 0.15 logMAR from previous ATS studies.³⁷⁻³⁹ The 95% confidence interval for the standard deviation was 0.13 to 0.16 logMAR. These were used to compute sample sizes in the table below:

**Total Sample Size Estimates
Based on 90% Power***

Standard Deviation (logMAR)	Noninferiority Limits (difference in logMAR)			
	0.050	0.055	0.060	0.075
0.13	234	194	164	106
0.14	270	224	188	122
0.15	310	258	216	140
0.16	354	292	246	158

* Based upon alpha = 0.05 for 1-sided t-test. Cells reflect total sample size needed

Based on a standard deviation of 0.15 logMAR, a sample size of 310 subjects was chosen (155 per group) in order to have 90% power for a non-inferiority hypothesis test, assuming that the true difference between the two treatments is zero with a non-inferiority limit of 0.05 logMAR. A total sample size of 346 (173 per group) was computed after adjustment for 10% loss to follow-up.

Interim Monitoring

There are no plans to conduct interim monitoring for efficacy and/or futility given there are no safety concerns or health risks with either treatment, and subjects will have access to the alternate treatment after completing the study. In addition, based on pilot data of binocular therapy in this age group³⁵, it is unlikely that the treatment effect of patching is sufficiently superior to binocular therapy to allow criteria for futility stopping to be met at an interim analysis. Finally, early stopping for efficacy would reduce power for the planned test of superiority of binocular therapy in the event that binocular treatment is declared non-inferior to patching.

5.2.2 Older Cohort (Children 13 to <17 years of age)

The standard deviation for change in amblyopic eye visual acuity at 16-weeks was estimated to be 9.0 letters from previous ATS studies.²⁰ The 95% confidence interval for the standard deviation was 5.8 to 10.1 letters. These were used to compute sample sizes in the table below:

Standard Deviation (letters)	Mean Change from Baseline in Visual Acuity at 16-weeks (letters)		
	3.75	5.0	6.25
6.0	110	64	42
7.0	150	86	56
8.0	194	110	72
9.0	246	140	90
10.0	302	172	110

* Based upon alpha = 0.05 for 2-sided t-test. Cells reflect total sample size needed

Based on a standard deviation of 9 letters, a sample size of 140 subjects was chosen (70 per group) in order to have 90% power to detect a treatment group difference if the true difference in mean visual acuity change between treatment groups is 5.0 letters (1 line) at 16 weeks. Adjusting for 10% loss to follow-up, a total sample size of 156 (78 per group) is needed.

Interim Monitoring

Interim monitoring for futility will be conducted for the older cohort. Although there is some evidence to suggest that binocular treatment may be better than patching in older children, the potential for poor compliance with binocular treatment in this age group is a concern, and could increase the chance that binocular treatment cannot be demonstrated to be better than patching.

Guidelines and provisions for futility stopping will be established prior to any tabulation or analysis of outcome data. Details of the interim monitoring plan will be developed in consultation with the DSMC and will be included in the statistical analysis plan. A sample size adjustment of 5% will be applied to account for loss of power due to interim futility monitoring, resulting in a final sample size of 166 subjects (83 per group).

5.3 Primary Analysis

Two treatment approaches will be evaluated within each of the age cohorts as follows:

1. Binocular treatment: Binocular computer game play 1 hour per day, 7 days per week (minimum of 4 days per week)
2. Patching treatment: Patching 2 hours per day, 7 days per week

An analysis of covariance (ANCOVA) will be performed to compute the 16-week mean change in visual acuity for each treatment group, adjusted for baseline acuity and baseline age, and a 95% confidence interval will be constructed on the treatment group difference. Linearity assumptions will be evaluated for baseline visual acuity and baseline age and these factors will be treated as continuous covariates if the model assumptions are met.

For the younger age cohort (5 to <13 years of age), the upper limit of a 1-sided 95% confidence interval on the treatment effect (Patching – Binocular treatment) will be compared with the non-

inferiority limit of 0.05 logMAR. Non-inferiority of binocular treatment will be declared if the upper 1-sided confidence interval limit is less than the non-inferiority margin of 0.05 logMAR. In the event that non-inferiority of binocular treatment is declared, a test for superiority of binocular treatment will be performed using the same 95% confidence interval and pre-specified margin.

For the older age cohort (13 to <17 years of age), superiority of binocular treatment will be declared if the treatment effect (Binocular treatment – Patching) is positive and the 95% confidence interval on the treatment group difference in mean visual acuity change excludes zero.

The primary analysis will follow the intent-to-treat principle. Data will be included only from subjects who complete the 16-week exam within the predefined analysis window. There will be no imputation of data for subjects who are lost to follow-up or withdraw from the study prior to the 16-week exam. In a secondary approach to the primary analysis, multiple imputation for missing data will be performed and results of the analysis with imputation of missing data assessed for consistency with the primary analysis. A separate analysis also will be conducted including only subjects whose outcome exams were performed within the protocol time window for the visit.

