All subjects will be seen at 4, 8, 12, and 16 weeks after randomization. Subjects achieving amblyopic-eye visual acuity equal to or better than the fellow-eye visual acuity (0 or more lines better with ATS-HOTV, or 0 or more letters better with E-ETDRS) and at least 20/25 (or ≥ 78 letters if E-ETDRS) visual acuity in both eyes will be considered to have resolved and will discontinue treatment, although these subjects will still return for all remaining follow-up exams. If at a subsequent visit there is regression of amblyopia (≥ 2 logMAR lines or ≥ 10 letters from the best previous visual acuity), treatment will be restarted.

At each follow-up visit, we will assess distance visual acuity in each eye using ATS-HOTV for children <7 years at enrollment and the E-ETDRS for children ≥ 7 years at enrollment. We will also assess stereoacuity using the Randot Butterfly Stereoacuity test and Randot Preschool Stereoacuity test, history of diplopia, and ocular alignment by cover uncover test, simultaneous prism cover test (SPCT) (if deviation present), and prism and alternate cover test (PACT).

Analysis

The primary analysis in the younger cohort (ages 5 to < 13 year) will be a non-inferiority analysis of mean visual acuity change from enrollment at 16 weeks in the binocular computer treatment group compared with the patching group. The primary analysis in the older cohort (ages 13 to < 17 years) will be a superiority analysis of mean visual acuity change from enrollment at 16 weeks in the binocular treatment group compared with the patching group.

Study Summary Flow Chart

CHAPTER 2: SUBJECT ENROLLMENT

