2.4 Procedures at the Enrollment Visit

All examination procedures must be tested within 7 days prior to the date of enrollment, except the cycloplegic refraction and ocular examination, which may be performed within 7 months prior to enrollment. All examination procedures at enrollment are performed in the subject's current correction, if required (testing in trial frames is not permitted), and without cycloplegia:

1. Distance Visual Acuity Testing: Monocular distance visual acuity testing will be performed in current refractive correction (if required) in each eye by a certified examiner using the electronic ATS-HOTV visual acuity protocol for children <7 years and the E-ETDRS visual acuity protocol for children ≥ 7 years on a study-certified acuity tester displaying single surrounded optotypes as described in the *ATS Testing Procedures Manual*.
 - Testing must be completed without cycloplegia and with spectacles or contact lenses, if worn (trial frames not allowed at enrollment)
 - The same visual acuity protocol will be used throughout the study regardless of age at follow-up.
2. Stereoacuity Testing:
 - Stereoacuity will be tested at near in current refractive correction using the Randot Butterfly and Randot Preschool stereoacuity tests.
3. Ocular Alignment Testing:
 - Ocular alignment will be assessed in current refractive correction by the cover/uncover test, simultaneous prism and cover test (SPCT), and prism and alternate cover test (PACT) in primary gaze at distance (3 meters) and at near (1/3 meter) as outlined in the *ATS Procedures Manual*.
 - See *section 2.2.1* for eligibility criteria related to ocular alignment.
4. Additional Clinical Testing:
 - Ocular examination as per investigator's clinical routine (if not performed within 7 months)
5. Nonius Cross Alignment
 - Subjects will be tested to see if they are able to align the nonius cross presented on the iPad. Subjects unable to fuse the cross are not eligible for the study.
6. Demonstration of Game Understanding
 - Subjects must demonstrate that they understand the game by scoring at least one completed line while playing the game set to the easy level in the office. Subjects unable to score a line are not eligible for the study.

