2.5 Randomization of Eligible Subjects

The Jaeb Center will construct a Master Randomization List using a permuted block design stratified by site and age subgroup (5 to <7 years versus 7 to <13 years) in the younger cohort (5 to <13 years), and stratified by site and baseline amblyopic-eye visual acuity (20/40 to 20/80 (53 to 72 letters) and 20/100 to 20/200 (33 to 52 letters)) in the older cohort (13 to <17 years), which will specify the order of treatment group assignments. Although we would ideally stratify by each of three factors (site, age subgroup, and baseline amblyopic acuity) in both the younger and older cohorts, this was unlikely to achieve the desired balance given the proposed sample size, and so the

2 most important factors were chosen, within each age cohort, for stratification. Randomization will not be stratified by presence of a tropia since diagnosis of a microtropia is problematic.

All eligible subjects enrolled in the study will be randomly assigned in a 1:1 allocation to one of the following groups for each of the age cohorts:

1. Binocular treatment group: binocular computer game play 1 hour per day, 7 days per week (minimum of 4 days per week)
2. Patching group: Patching 2 hours per day, 7 days per week.

Once a child is assigned to treatment, he/she will be included in the analysis regardless of whether or not the assigned treatment is received. Thus, the investigator must not randomly assign a subject to treatment unless convinced that the parent will accept either of the treatments.

CHAPTER 3: TREATMENT AND FOLLOW-UP

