5.4.1 Visual Acuity Defined as a Binary Outcome

Secondary analyses will estimate the proportion of subjects who achieve the following visual acuity outcomes by treatment group:

1. Amblyopic-eye visual acuity improvement of 2 or more logMAR lines (10 or more letters if E-ETDRS) 16 weeks after randomization
2. Resolution of amblyopia at 16 weeks after randomization, defined as amblyopic-eye visual acuity of 20/25 or better (≥ 78 letters) and within 1 logMAR line (≤ 5 letters) of the fellow-eye acuity.

The proportion of subjects who achieve each outcome will be tabulated by treatment group and an exact 95% confidence interval will be computed on the group proportion. A p-value for the treatment group comparison will be computed using binomial regression with adjustment for baseline visual acuity. If the binomial regression model does not converge, Poisson regression with robust variance estimation or an exact method (without baseline adjustment) will be used to derive a p-value for the treatment group comparison.

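### The primary ANCOVA omits site, and captures the younger cohort's age stratum only partly, although randomisation is stratified on both: a small, conditional loss of precision

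*Protocol*

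**What the plan says.** Section 2.5 (Randomization of Eligible Subjects) describes permuted blocks "stratified by site and age subgroup (5 to <7 years versus 7 to <13 years) in the younger cohort". For the older cohort the list is "stratified by site and baseline amblyopic-eye visual acuity", the latter in two bands. It explains that three factors would be too many for the sample size, so the "2 most important factors were chosen, within each age cohort, for stratification".

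Section 5.3 (Primary Analysis) specifies, for both cohorts, an ANCOVA for the "16-week mean change in visual acuity for each treatment group, adjusted for baseline acuity and baseline age". Linearity is to be checked, and "these factors will be treated as continuous covariates if the model assumptions are met". The form to be used if the check fails is not stated. Site is not mentioned, and neither is the younger cohort's age-stratum indicator.

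The acuity method depends on age at the same cut. Section 1.4 describes follow-up testing "using ATS-HOTV for children <7 years at enrollment and the E-ETDRS for children ≥ 7 years at enrollment", and section 2.4 keeps the enrolment method for the whole study.

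Among the secondary analyses, the p-value for the binary acuity outcomes in section 5.4.1 is "computed using binomial regression with adjustment for baseline visual acuity", without age. Section 5.4.7.1 likewise adjusts fellow-eye change for baseline acuity only.

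**The concern.** Stratified randomisation balances the arms on the stratifying factors. If such a factor predicts outcome and is left out of the model, its variance stays in the residual. The treatment difference itself is more precise than the model reports, so the model-based standard error is too large and the interval too wide. The protocol ranks site and the age subgroup as the two factors that matter most in the younger cohort, then leaves site out of the analysis without giving a reason. This is not simply a detail left for the statistical analysis plan, because section 5.3 names the covariates.

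The age stratum needs separate thought because it also marks which acuity test a child receives. A straight line in age cannot represent a jump at 7 years, if there is one.

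What is at stake is precision against a narrow non-inferiority margin of 0.05 logMAR in the younger cohort, and against a 5-letter difference in the older one. Bias is not at issue.

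**Working it through.** **Inputs from the protocol.** Younger cohort (5.2.1): SD of change 0.15 logMAR, margin 0.05, true difference 0, one-sided alpha 0.05, 90% power, 155 per group. Older cohort (5.2.2): SD 9.0 letters, difference 5.0 letters, two-sided alpha 0.05, 90% power, 70 per group. Allocation is 1:1.

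**Inputs not in the protocol, assumed here.** Site ICC of the outcome (0 to 0.10), number of sites (25 or 60), block size (4), age distribution, and size of any step at age 7.

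**1. The plan's own sample sizes.** A noncentral-t calculation with the unadjusted SD reproduces every cell of both sample-size tables, including 310 and 140. Allowance for loss: 155/0.9 = 172.2, so 173 per group and 346 in total; 70/0.9 = 77.8, so 78 per group and 156 in total. Futility allowance: 78/0.95 = 82.1, so 83 per group and 166 in total. The planned power therefore never relied on adjusting for site or stratum.

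**2. Site, upper bound on the gain.** With full balance within site and no cost in degrees of freedom, the standard error is multiplied by √(1 − ICC). In the younger cohort the unadjusted value is 0.15 × √(2/155) = 0.01704.

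| Assumed ICC | SE with site (younger) | Reduction in SE | Younger power, n = 310 | Older power, n = 140 |
|---|---|---|---|---|
| 0 | 0.01704 | 0% | 90.0% | 90.4% |
| 0.02 | 0.01687 | 1.0% | 90.5% | 90.9% |
| 0.05 | 0.01661 | 2.5% | 91.3% | 91.8% |
| 0.10 | 0.01616 | 5.1% | 92.5% | 93.1% |

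Under the same idealised balance, leaving site out would make the true one-sided size 1 − Φ(1.645/√(1 − ICC)): 4.8%, 4.6% and 4.2% at ICC 0.02, 0.05 and 0.10.

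**3. Site, by simulation.** With 310 children in 25 or 60 sites, blocked within site and age stratum, a random intercept for site plus the age-stratum indicator lost no precision at ICC 0. It reduced the standard error by about 1%, 2% and 4% at ICC 0.02, 0.05 and 0.10. The realised gain is a little below the bound because balance within small sites is incomplete.

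Fixed site effects behave differently. One-sided 95% half-widths (logMAR), against the protocol model:

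| Sites | ICC 0 | ICC 0.05 | ICC 0.10 |
|---|---|---|---|
| 25 | 0.0285 vs 0.0281 | 0.0278 vs 0.0281 | 0.0270 vs 0.0281 |
| 60 | 0.0294 vs 0.0282 | 0.0286 vs 0.0281 | 0.0279 vs 0.0282 |

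With 60 sites, fixed effects widen the interval unless the ICC is near 0.10.

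The simulated one-sided type I error of the protocol model was 0.044 to 0.056. With 1,500 runs per scenario, Monte Carlo error is about ±1.96 × √(0.05 × 0.95/1500) = ±0.011, so this is compatible with 0.05 and with slight conservatism.

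**4. Age stratum, beyond linear age.** Assume ages uniform from 5 to 13. The share under 7 is 0.25, so the indicator's variance is 0.25 × 0.75 = 0.1875. Mean ages in the two strata are 6 and 10, so its covariance with age is 0.1875 × 4 = 0.75 in absolute value. The variance of age is 8²/12 = 5.33. Linear age therefore explains 0.75²/(0.1875 × 5.33) = 0.56 of the indicator. With half the children under 7 the figure is 0.71.

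A 0.05 logMAR step leaves 0.1875 × (1 − 0.56) × 0.05² = 0.0002 of variance, against 0.15² = 0.0225, or about 0.9%. Not fitting it widens the interval by 0.4 to 0.5% across the two age mixes. Steps of 0.02, 0.03 and 0.10 give about 0.1%, 0.2% and 1.7 to 1.9%.

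**5. Older cohort's second factor.** Baseline acuity is already a covariate, so only site is missing there.

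**The case against.** The case against acting is substantial. Age is in the model, and so is the older cohort's acuity factor; only site is wholly absent. Section 5.3 already provides a linearity check, and Chapter 5 describes itself as a summary with detail to follow in an analysis plan. The ICC is unknown and could be zero. Modelling many small sites can cost more than it gains. Any error from omission is in the conservative direction, which is the safe one for a non-inferiority claim.

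Most of this stands and limits the size of the point. The many-sites argument applies to fixed effects; a random intercept lost nothing at ICC 0.

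Three stronger readings are tempting, and the protocol supports none of them:

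- **Power falls short of 90%, or the test is invalid.** The sample sizes come from the unadjusted SD, so the stated power is not missed. What is forgone is a possible bonus.
- **A step at age 7 is likely because the test changes there.** The outcome is change within a child and the method is kept throughout, so a constant offset between the two tests cancels. A step would need the two tests to differ in responsiveness, or response to change abruptly at that age. The protocol shows neither.
- **The secondary models are deficient for omitting age.** Sections 5.4.1 and 5.4.7.1 do omit it, but no loss has been quantified, and extra terms may aggravate the convergence problem that section 5.4.1 already anticipates.

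**Conclusion.** The mismatch between design and analysis is real: site is a stratification factor in both cohorts and appears in neither primary model, and the younger cohort's age stratum enters only through continuous age. The consequence is a minor loss of efficiency that depends on site predicting outcome. It is nil at ICC 0 and reaches about 4 to 5% of the standard error at ICC 0.10, or 0 to about 2.5 power points in the younger cohort. The age-stratum term is worth under 0.5% for any step up to 0.05 logMAR. The ICCs, site numbers, age mixes and step sizes are all assumptions; the direction, conservative or neutral, does not depend on them. It is worth correcting because it costs no patients and settles the model before outcomes are seen, not because the planned analysis is unsound.

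**What to change.** In section 5.3, add site as a random intercept in both cohorts, and the randomisation age-stratum indicator (5 to <7 / 7 to <13) in the younger cohort. Keep baseline acuity and age as continuous covariates. State that the site term is dropped if its variance is estimated as zero, and do not use fixed effects for many small sites. The older cohort needs no acuity-stratum term, since baseline acuity covers it. If the sponsor prefers the present model, one line giving the reason would do. Carrying age and the stratum into sections 5.4.1 and 5.4.7.1 is optional.

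The cost is about one sentence of protocol text, with no change to sample size, data collection or conduct.

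### The younger cohort's follow-on superiority test is fixed wrongly: it reuses the 0.05 logMAR non-inferiority margin, names no zero threshold and leaves the interval's sidedness unclear

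*Protocol*

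**What the plan says.** All the decision rules are in Protocol section 5.3, Primary Analysis.

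- **General model (both cohorts).** An ANCOVA compares 16-week change, and "a 95% confidence interval will be constructed on the treatment group difference". Sidedness is not stated.
- **Younger cohort, non-inferiority.** The quantity judged is "the upper limit of a 1-sided 95% confidence interval on the treatment effect (Patching – Binocular treatment"). Non-inferiority is declared if that limit is below 0.05 logMAR.
- **Younger cohort, superiority.** If non-inferiority is declared, "a test for superiority of binocular treatment will be performed using the same 95% confidence interval and pre-specified margin".
- **Older cohort, superiority.** The effect, here binocular minus patching, must be positive and "the 95% confidence interval on the treatment group difference in mean visual acuity change excludes zero".

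The sample size tables in section 5.2 give alpha as 0.05 one-sided for the younger cohort (5.2.1) and 0.05 two-sided for the older cohort (5.2.2). Section 5.2.1 also treats the younger cohort's superiority test as a planned step: one reason given for having no interim look is that early efficacy stopping "would reduce power for the planned test of superiority of binocular therapy".

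**The concern.** A superiority claim is normally judged against zero. The younger cohort's rule points instead to a pre-specified margin, and the only one in the protocol is the non-inferiority margin. The next paragraph, for the older cohort, states the correct form, so the protocol has the right rule available and does not use it here. Section 5.4 does refer to the ordinary no-difference null, but only for secondary analyses, so it does not repair a rule placed under Primary Analysis.

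The interval is unclear too. The nearest 95% interval is the one-sided one in the same paragraph. The ANCOVA paragraph above it describes a 95% interval with no stated side, and that could also be the one meant.

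At stake is whether the trial can claim that binocular treatment is better than patching in 5- to <13-year-olds. Two analysts following this sentence could reach opposite conclusions from the same data.

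**Working it through.** **Inputs (Protocol 5.2.1 and 5.3).** SD of change 0.15 logMAR; 155 per group analysed; non-inferiority margin 0.05; one-sided alpha 0.05; power 90% at a true difference of 0; 10% loss to follow-up.

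**Reproducing the plan's figure.** n per group = 2 × (1.645 + 1.282)² × 0.15² / 0.05² = 154.2, rounded up to 155, or 310 in total. Then 155 / 0.9 = 172.2, rounded up to 173 per group, or 346. Both figures agree with the protocol. The exact t calculation also gives 310 and reproduces all 16 cells of the 5.2.1 table.

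**Standard error.** SE = 0.15 × √(2/155) = 0.01704 logMAR, with 308 degrees of freedom. The upper limit lies 0.0281 above the estimate for a one-sided 95% limit and 0.0335 above it for a two-sided 95% interval.

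**Probability of declaring superiority.** Let δ be the true patching minus binocular difference, with change counted as improvement, so that negative values favour binocular. For a threshold c,

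P(upper limit < c) ≈ Φ((c − δ)/SE − z), with z = 1.645 (one-sided) or 1.960 (two-sided).

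- Threshold +0.05, one-sided, δ = 0: Φ(2.934 − 1.645) = 0.90.
- Threshold −0.05, one-sided, δ = −0.05: Φ(0 − 1.645) = 0.05.
- Threshold 0, two-sided, δ = −0.05: Φ(2.934 − 1.960) = 0.835.

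The table uses the exact noncentral t, which differs only slightly (0.833 in place of 0.835).

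| Reading of the rule | Observed patching minus binocular must be below | Declared if arms are identical | Declared if binocular is truly better by 0.05 |
|---|---|---|---|
| One-sided limit < +0.05 | +0.0219 | 90.0% | about 100% |
| One-sided limit < −0.05 | −0.0781 | about 0.0002% | 5.0% |
| One-sided limit < 0 | −0.0281 | 5.0% | 90.0% |
| Two-sided 95% limit < 0 | −0.0335 | 2.5% | 83.3% |

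The first row is the non-inferiority rule again. It would be met by small observed differences in favour of patching, and in 42.8% of trials in which patching is truly better by 0.025. The second row asks for superiority by at least half a line (0.05 logMAR); power reaches 90.0% only at a true advantage of 0.10.

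**Sign of change.** Section 5.3 does not say how change is coded. If improvement is positive, both rules are coherent: patching minus binocular below 0.05 means binocular is not much worse, and binocular minus patching above zero means binocular is better.

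**The case against.** The strongest defence is that context shows zero was meant. A superiority test that passed whenever non-inferiority passed would not be a further test, and section 5.2.1 speaks of that test having power of its own. The ANCOVA interval read as two-sided and set against zero gives the conventional 2.5%. The cohort's stated objective and its sample size also rest on non-inferiority alone, and that rule is explicit.

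Much of this stands. A reader might infer that the protocol must either hand out superiority automatically or double the error rate. The documents do not support that. The text also admits the conservative reading (superiority by 0.05) and the two-sided reading against zero. The 5% from a one-sided limit against zero equals this cohort's own stated alpha; it is double only when compared with the older cohort's two-sided 0.05. The 90% figure shows what the literal wording permits and is not a forecast of what the analysts would do.

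A reader might also infer that, because improvement lowers logMAR and the subtraction order changes between cohorts, the rule could reward the worse arm. That is not shown. The protocol does not define change as follow-up minus baseline. It reports gains as positive amounts elsewhere (sections 1.1 and 5.4.1), and both rules make sense on that coding.

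Context does not remove the defect, however. To reach the sensible rule, the analyst has to disregard the words about the margin and choose a side for the interval. The protocol has not left these points to the SAP; it has stated them, and stated them wrongly.

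**Conclusion.** The point holds for the younger cohort's follow-on superiority test. Its threshold is wrongly fixed by reference to the non-inferiority margin, and the sidedness of its interval is not determined. Depending on the reading, the chance of declaring superiority when the arms are identical runs from practically 0 to 90%. With zero as the threshold it is 5% or 2.5%, according to sidedness.

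These figures assume 155 analysed per group and SD 0.15 logMAR, as the protocol plans. They take no credit for precision gained from covariate adjustment.

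The non-inferiority margin, limit and declaration rule are not affected, nor are the sample size calculation and the older cohort's rule. The coding of change needs at most a clarifying clause.

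**What to change.** Replace the superiority sentence in section 5.3 with: *If non-inferiority is declared, superiority of binocular treatment will be declared if the upper limit of the two-sided 95% confidence interval for (Patching − Binocular) is below 0.* This matches the older cohort's rule. Carry the same wording into the SAP before outcome data are analysed.

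As a minor clarification, add: *Change is coded as improvement, that is, enrollment logMAR minus 16-week logMAR.*

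The cost is two sentences. Superiority power at a true 0.05 logMAR advantage is about 83%, against 90% with a one-sided limit set against zero. The sample size and the non-inferiority test stay as they are. No alpha adjustment is needed, because superiority is tested only after non-inferiority has been declared, in a fixed sequence.
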